#### 4.2 Rescue medication or emergency treatment

There exists no special rescue medication in this trial. Children with interstitial lung disease often are very sick. So far we do not know which patient will benefit from the use of hydroxychloroquine and which will not. It is possible, that some patients will deteriorate during the trial. As no evidence based standards for treating interstitial lung disease in children exist, it is in the responsibility of the treating physician to decide, what the further treatment will be.

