#### 8.3.1 Definition and analysis of primary outcome

The oxygenation of the patient is the primary outcome variable. The primary outcome will be assessed as the response rate of oxygenation to the intervention. As the patient's respiratory condition can vary over a broad range, may necessitate variable external support, and as these changes may occur over relatively short time periods, it is necessary to take all this into consideration when assessing oxygenation. Therefore we defined the parameters to be measured depending on the patient's condition to define a responder (Table 3.8-1). The majority of children included into the study are expected to be on supplemental oxygen or in room air. In these subjects oxygen saturation in room air will be assessed (for assessments please see 3.2). However to include the broad continuum of respiratory support possible in individual patients, an approach was chosen accommodating that need. Responses to treatment judged as significant were defined depending on Patient's condition. How and when to assess the variables is further detailed in the study protocol.

Oxygenation, the primary outcome parameter, was chosen as a dichotomous variable (response yes or no). Its components, i.e. O2-saturation and respiratory rate, are also used continuously in a descriptive manner as secondary outcome variables.

Tab 3.8-1: Definition of responders to treatment depending on Patient's condition

Patient's condition	Measured parameters	Specific metric	Definition of significant change or responder to the initiation of HCQ	Definition of significant change or responder to the withdrawal of HCQ	Method of aggregation
In room air	In room air O2 Sat (mean value) Respir rate (mean value)	Change from baseline	Increase $\geq 5\%$ in O2 Sat, or Decrease in resp. rate $\geq 20\%$	Decrease $\geq 5\%$ in O2 Sat, or Increase in resp. rate $\geq 20\%$	Proportion of responders
On O2-supplement	In room air O2 Sat (mean value) Respir rate (mean value)	Change from baseline	Increase $\geq 5\%$ in O2 Sat or Decrease in resp. rate $\geq 20\%$ or Support no more needed	Decrease $\geq 5\%$ in O2 Sat, or Increase in resp. rate $\geq 20\%$ or Support newly needed	Proportion of responders
On high-flow nasal cannula	O2-flow, air-flow	Change from baseline	Decrease $\geq 20\%$ or Support no more needed	Increase $\geq 20\%$ or Support newly needed	Proportion of responders

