Ventilated	Oxygenation index	Change from baseline	Decrease $\geq 20\%$ or Support no more needed	Increase $\geq 20\%$ or Support newly needed	Proportion of responders

The definition of the threshold for a significant change or responder regarding oxygenation will be further assessed as a secondary outcome.

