6.6 Primary Analysis

The variable assessing the primary outcome is the response rate measured by the oxygen saturation in room air.

START HCQ block

Relative change from trial day 1 (Visit 2) to day 28 (Visit 3) and day 56 (Visit 4) and from day 28 to day 56 change from active compound compared to change from placebo

STOP HCQ block

Relative change from trial day 1, i.e. Visit 2, through day 84, i.e. Visit 5: change from active compound compared to change from placebo

Both blocks separately

a) A difference between the changes in placebo and active phases is considered significant as described in the table below.

Patient's condition	Measured parameter	Definition of significant change or responder
Stable in room air or on	SpO2 in room air	Increase $\geq 5\%$

O2-supplement		
On high-flow nasal cannula	O2-flow, air-flow	Decrease $\geq 20\%$ or support not needed any more
Ventilated	Oxygenation index	Decrease $\geq 20\%$ or support not needed any more
On ECMO		Decrease $\geq 20\%$ or support not needed any more

The analysis will be done first by discarding the information on the patient's condition. Descriptive analyses will be done overall and for all patients conditions separately.

b) Patients are defined as responder as described in the table above. The numbers of responders are counted and compared by Fisher's exact test as well as logistic regression models with factors for treatment group and age group.

The following SAS code can be used:

```
PROC LOGISTIC DATA=indata;
  CLASS treatment age_gr;
  MODEL responder_YN = treatment age_group treatment*age_group;
RUN;
```

Both blocks together

Not applicable. There were too few patients in both blocks.

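### The START responder rule has no provision for a child who moves up to a higher level of respiratory support, so a treatment failure can be scored as a response or drop out of the comparison

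*SAP*

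**What the plan says.** The responder table in SAP 6.6 has one row per type of support. For high flow (oxygen flow and air flow), ventilation (oxygenation index, OI) and ECMO (no parameter named) the criterion is "Decrease $\geq 20\%$ or support not needed any more". For children in room air or on supplemental oxygen it is only a rise of at least 5% in room-air saturation. The table alone decides: "Patients are defined as responder as described in the table above". The first analysis pools the rows: "The analysis will be done first by discarding the information on the patient's condition".

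Tab 3.8-1 in protocol 8.3.1 gives the same initiation rule for high flow and ventilation, "Decrease $\geq 20\%$ or Support no more needed", and has no ECMO row. For withdrawal it names worsening in those two rows: "Increase $\geq 20\%$ or Support newly needed". The initiation column has no matching statement that worsening is non-response.

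SAP 5.1 plans no substitution of missing values. SAP 6 treats a value as missing when the visit took place but nothing was documented, and by default bases percentages on non-missing data.

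The protocol expects such changes. Section 8.3.1 says that a patient's condition "may necessitate variable external support, and as these changes may occur over relatively short time periods", and section 4.2 says: "It is possible, that some patients will deteriorate during the trial".

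**The concern.** Each row measures a quantity that belongs to one device or mode of support. When a child moves to a higher mode, that quantity can fall, or cease to be measured, because the device changed and not because the lung improved. The rule sets no condition on the level of support at follow-up, and neither document says whether the row is fixed at Visit 2 or taken at the endpoint visit.

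At stake is the primary responder count in START. A child who deteriorated enough to be ventilated or put on ECMO should count against the arm. As the rule stands, that child may count in its favour or may leave the denominator. If HCQ works and escalation is therefore more frequent on placebo, scoring escalated children as responders would shrink the observed difference.

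**Working it through.** The plan has no figure to reproduce. Protocol 8.1 gives a target of 80 without a formal calculation, response rates or power.

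**1. Arm size.** 80 planned (protocol 8.1), equal split between blocks expected (protocol 3.2), 1:1 allocation (protocol 3.5.1): 80 / 2 / 2 = 20 per START arm. One child is 1/20 = 5 percentage points.

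**2. High flow to ventilation.** If cannula flow is entered as 0, the change is (0 − x)/x = −100% and the 20% criterion is met. If flow is left blank, there is no change to score. A blank is plausible, because the protocol's list of parameters for ventilated patients (schedule footnote m) does not include cannula flow. The documents do not settle which happens.

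**3. Ventilation to ECMO.** OI = FiO2 × MPAW / PaO2 (SAP 4.2). With FiO2 and MPAW unchanged, OI falls by 20% once PaO2 rises by a factor of 1/0.8 = 1.25. All settings below are assumptions for illustration, starting from FiO2 0.8, PaO2 55, rate 40, inspiratory time 0.5, PIP 28, PEEP 8:

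| After the move | Change in OI | 20% fall met? |
|---|---|---|
| PaO2 55 to 70 only | 55/70 − 1 = −21.4% | yes |
| FiO2 0.8 to 0.6 only | 0.6/0.8 − 1 = −25.0% | yes |
| Rate 10, inspiratory time 1, PIP 20, PEEP 10, FiO2 0.4, PaO2 70 | −86% | yes |
| PaO2 55 to 45 only | 55/45 − 1 = +22.2% | no |

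The third row uses MPAW as printed: 9.33 falls to 3.33, so OI goes from 0.8 × 9.33/55 = 0.136 to 0.4 × 3.33/70 = 0.019. With the usual form, (rate × inspiratory time/60) × (PIP − PEEP) + PEEP, MPAW goes from 14.67 to 11.67 and OI from 0.213 to 0.067, a change of −69%. The criterion can therefore be met, but need not be.

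**4. Room air or supplemental oxygen to higher support.** The SAP row needs a room-air saturation at the endpoint. Protocol Table 3.3-1 specifies flows for high flow and OI for ventilation, not room-air saturation. Such a child may have no usable value and drop out. The SAP row has no support clause through which the child could become a responder.

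**5. Effect on the Fisher test.** Assumed true counts, HCQ v placebo, with k escalated placebo non-responders (two-sided p):

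| True counts | k = 0 | k = 1 | k = 2 | k = 3 |
|---|---|---|---|---|
| 7/20 v 1/20, scored as responders | 0.044 | 0.127 | 0.273 | 0.480 |
| 8/20 v 1/20, scored as responders | 0.020 | 0.065 | 0.155 | 0.301 |
| 7/20 v 1/20, dropped as missing | 0.044 | 0.044 | 0.045 | 0.048 |

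Dropping a child changes the placebo rate only from 1/20 = 5.0% to 1/19 = 5.3%. In this example the scoring route drives the result. The drop-out route has little effect on p but loses treatment failures from a population defined as all randomised children.

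**6. How many children.** The documents give no share on high flow or ventilation and no escalation rate. If 10–30% of the 40 START children begin there, and 10–30% of those escalate and are all scored as responders, the expected number is between 40 × 0.1 × 0.1 = 0.4 and 40 × 0.3 × 0.3 = 3.6 over both arms. Both ranges are assumptions.

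**The case against.** A reader might infer that any escalated child automatically meets the clause on support no longer being needed. The documents do not support that. A ventilated child still needs support, and the clause is met only if support means that row's device. The withdrawal column, which names newly needed support as worsening, shows that the clause is meant as improvement.

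A reader might also infer that a move from low-flow oxygen to high flow scores as a response. That needs the support clause in the protocol's oxygen row and the same device-only reading. The corresponding SAP row has no such clause.

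Other points on the plan's side stand in part. Few children are exposed to the scoring route: "The majority of children included into the study are expected to be on supplemental oxygen or in room air". Entry requires stability, with less than 20% change in key parameters for those on respiratory support (protocol 3.6.1), and the main START comparison is at 28 days. SAP 4.1 lists only saturation for the ECMO state, so OI might not be applied there at all. The trial is exploratory, descriptive results by patient condition are planned, and the exacerbation record asks about an added level of ventilatory support, so such cases could be found afterwards.

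These points limit the size but do not supply the missing rule. The percentage branch does not depend on how the support clause is read. Where no value exists, the child is lost instead of being counted as a failure. Descriptive tables by condition do not change how a child is scored.

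**Conclusion.** The gap is real and sits in the primary endpoint. For START, neither document says how to score a child who moves to a higher support category, and the rule as written can count that child as a responder or leave the child out. The size cannot be derived from the documents. The firm figure is about 5 percentage points of an arm's rate per child scored as a responder, which rests on the planned 20 per arm. The p-values, OI examples and expected counts rest on assumed inputs and show only that one or two children could change how the result reads.

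A reader might infer that the trial is biased towards no effect. That follows only if HCQ works, escalation is more frequent on placebo and the escalated children are scored as responders. The documents establish none of these.

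**What to change.** Add one paragraph to SAP 6.6, with matching text in protocol 8.3.1:

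- Fix each child's support category at Visit 2.
- In the high-flow, ventilated and ECMO rows, define support no longer needed as a move to a lower level of support.
- Apply the 20% rule only when the category is the same at baseline and at the endpoint visit.
- For START, score a move up to high flow, ventilation or ECMO, or death, by the endpoint visit as non-response and not as missing.
- Name the parameter for the ECMO row.

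Leave the saturation rule unchanged for children who remain in room air or on supplemental oxygen. A blanket rule that every step down is a response and every step up a non-response would rewrite that row, where the scoring error does not arise.

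The cost is a small change to the endpoint derivation and its code, and slightly lower response counts. Oxygen demand, ventilation and extracorporeal support are already scheduled at every visit, so no new data are needed. The change concerns scoring only and leaves clinical care as it is.

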Statistical analysis	START HCQ block and STOP HCQ block The variable assessing the primary outcome is the response rate measured by the oxygen saturation in room air. Both blocks separately a) A difference between the changes in placebo and active phases is considered significant, if the oxygen saturation increases by $\geq 5\%$ . b) Patients are defined as responder if the oxygen saturation is increased by 5% compared to baseline. The numbers of responders are counted and compared by Fisher exact test. Both blocks together c) oxygen saturation and the correspondent responder will be analysed by a linear mixed model (or logistic regression respectively). If indicated, a Bayesian approach will be employed. If appropriate, the analyses will be adjusted for the stratification factor of the randomization: age group.

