## 6 TRIAL METHODS

### 6.1 Assessment of efficacy

The primary outcome of the trial is the oxygen saturation, measured in room air. As the numbers of subjects that will be included into the trial will be low and cannot precisely be predicted, a spectrum of secondary outcome parameters will be interpreted exploratory, including patient oriented measures and outcomes, like quality of life.

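### The protocol defines the STOP-block responder in two opposite directions, and SAP 6.6 carries the improvement-only one into the primary responder test, which then cannot register worsening after withdrawal

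*SAP*

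**What the plan says.** **Protocol 8.3.1, Tab 3.8-1.** The table has one column for response to initiation of HCQ and another for response to its withdrawal. The withdrawal column is a deterioration in every row. For patients on supplemental oxygen it reads "Decrease $\geq 5\%$ in O2 Sat, or Increase in resp. rate $\geq 20\%$ or Support newly needed". For high-flow and ventilated patients it reads "Increase $\geq 20\%$ or Support newly needed". The room-air row has the saturation and respiratory-rate criteria only.

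**Protocol synopsis, Statistical analysis.** Under a heading that covers START and STOP, a patient is a responder "if the oxygen saturation is increased by 5% compared to baseline". No withdrawal version is given.

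**SAP 6.6.** Under the heading for both blocks analysed separately there is a single table. Room-air saturation must rise by at least 5%. The high-flow, ventilated and ECMO rows each read "Decrease $\geq 20\%$ or support not needed any more". Part b) then says "Patients are defined as responder as described in the table above" and names Fisher's exact test and a logistic model. The SAP contains no reversal for STOP.

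For STOP, SAP 6.6 also lists "Relative change from trial day 1, i.e. Visit 2, through day 84, i.e. Visit 5: change from active compound compared to change from placebo", without naming a test for it.

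**The concern.** Protocol section 3 describes STOP as a randomised withdrawal: patients already on HCQ either continue it or switch to placebo. If HCQ works, the expected signal is worsening on placebo. A responder variable that is positive only for improvement puts worsened and stable patients in the same category. The named primary tests could then show no difference between arms while other analyses in the same report show that withdrawal did harm. A reader would not know which result answers the STOP objective.

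**Working it through.** **1. The texts side by side, for STOP**

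| Condition | Protocol Tab 3.8-1, withdrawal | Protocol synopsis | SAP 6.6 |
|---|---|---|---|
| Room air | SpO2 down at least 5%, or respiratory rate up at least 20% | SpO2 up 5% | SpO2 up at least 5% |
| Supplemental oxygen | As room air, or support newly needed | SpO2 up 5% | SpO2 up at least 5% |
| High-flow | Flow up at least 20%, or support newly needed | not given | Flow down at least 20%, or support stopped |
| Ventilated | Oxygenation index up at least 20%, or support newly needed | not given | Index down at least 20%, or support stopped |
| ECMO | no row | not given | Down at least 20%, or support stopped; no measured parameter |

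The withdrawal column and the SAP table point in opposite directions in every row that they share. The synopsis sides with the SAP.

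**2. Inputs for the illustration**

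The documents give no event rates, alpha or power, so there is no planned figure to reproduce. Protocol 3.2 and 8.1 give 80 patients split equally between blocks, and 3.5.1 gives 1:1 allocation: 80/2/2 = 20 per arm. Two-sided alpha of 0.05 and all rates below are assumptions.

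**3. One worked example**

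Suppose 10/20 on placebo and 2/20 on HCQ worsen, and 2/20 in each arm improve.

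- Withdrawal coding compares 10/20 with 2/20. With the margins fixed (12 events in 40), P(k) = C(20,k)·C(20,12−k)/C(40,12). Summing the tables no more probable than the observed one (k = 0, 1, 2, 10, 11, 12) gives p = 0.0138.
- SAP coding compares 2/20 with 2/20, so p = 1.0.

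In the limiting case all 20 placebo patients worsen, no HCQ patient does, and nobody improves. SAP coding gives 0/20 against 0/20, p = 1.0. Withdrawal coding gives 20/20 against 0/20, p = 1.5 × 10⁻¹¹.

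**4. Rejection probabilities**

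These sum the product of the two binomial probabilities over all tables with Fisher p at or below 0.05.

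| Per arm | Withdrawal coding: HCQ 10% worsen, placebo 30 / 40 / 50 / 60% | SAP coding: 5 / 10 / 20% improve in both arms |
|---|---|---|
| 20 | 24 / 49 / 74 / 91% | 0.2 / 1.2 / 2.3% |
| 15 | 15 / 33 / 54 / 74% | 0.1 / 0.6 / 1.7% |
| 10 | 6 / 15 / 30 / 47% | 0.0 / 0.1 / 0.8% |

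The last column holds whatever the difference in worsening. If improvement itself differs between arms (placebo against HCQ, 20 per arm), the SAP test rejects in 1.7% of trials for 5% against 10%, 7.0% for 5% against 15%, and 17% for 0% against 15%.

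**5. How fragile the contrast is**

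SAP 5.1 substitutes no missing values, and protocol 3.6.3 allows withdrawal for life-threatening aggravation, so worsened patients may be the ones without a day-84 value. If 3 of the 10 worsened placebo patients lack day 84, withdrawal coding compares 7/17 with 2/20, p = 0.052. If 4 do, it compares 6/16 with 2/20, p = 0.10. At 10 per arm, 5/10 against 1/10 gives p = 0.14.

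**The case against.** **The SAP follows the synopsis.** True. A reader might infer that the SAP departed from the protocol on its own. The documents do not support that: the conflict lies inside the protocol and the SAP adopts one side. That changes where the correction is needed, but not the effect on STOP. Tab 3.8-1 is the only text that defines the responder separately for initiation and withdrawal.

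**Worsening remains visible elsewhere.** Also true. A reader might infer that the STOP block cannot detect harm from withdrawal at all. It can: SAP 6.6 keeps the relative change to day 84, and SAP 6.7.1 compares absolute saturation change, respiratory rate and oxygen requirement between arms. However, 6.6 names tests for the responder variable only. Item a) of 6.6 judges differences in change by the same improvement table, and which direction it intends for STOP is unclear.

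**The trial is exploratory.** Protocol 1.2 and 8.3 say so, and there is no formal sample size. This limits the consequence but does not justify scoring the primary variable against the direction of the design.

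**Correct coding might gain little.** With missing day-84 data or small arms this stands. A reader might infer that recoding would yield a significant STOP result. Nothing in the documents supports that, because every rate above is assumed.

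**It may be too late.** SAP 6.6 drops the combined analysis because "There were too few patients in both blocks". A reader might take this as proof of low enrolment. It could equally mean that few patients took part in both blocks. The past tense suggests that recruitment figures were known, but does not show that the blind was broken.

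**Conclusion.** The point holds, and it should be settled before the STOP responder result is reported. The protocol gives opposite responder definitions for STOP, and SAP 6.6 applies the improvement-only one, so the primary responder test in that block cannot register worsening. This follows from the wording alone and needs no assumption about rates. Its size depends on assumptions. At 20 per arm with complete data, assumed worsening of 50% against 10% would be detected with 74% power under withdrawal coding. The SAP rule rejects in at most 2.3% of trials at the equal improvement rates tried. The first figure falls to 30% at 10 per arm, and lower with selective loss of worsened patients. The damage is confined to interpretation of the STOP primary responder result. START and the other STOP comparisons are not affected by this reversal.

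**What to change.** Replace the shared table in SAP 6.6 with block-specific tables.

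- **START:** keep improvement.
- **STOP:** use the withdrawal direction of Tab 3.8-1: room-air saturation down at least 5% (room air or supplemental oxygen), flow up at least 20% on high-flow, oxygenation index up at least 20% if ventilated.
- State that fewer STOP responders on HCQ than on placebo favours HCQ.
- Align the protocol synopsis.

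Settle five open points in the same step, because copying Tab 3.8-1 would import them.

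1. **Respiratory rate.** Tab 3.8-1 includes it and the SAP 6.6 table omits it. SAP 4.2 lists it among the primary-variable assessments, while protocol 6.1 says "The primary outcome of the trial is the oxygen saturation, measured in room air".
2. **Newly needed support.** Define it by row. Tab 3.8-1 omits it for room-air patients, who could newly need support, and lists it for patients already on support.
3. **The 5% threshold.** Say whether it is relative (the outcome in protocol 3.3 and SAP 6.6 is a relative change) or absolute (as in inclusion criterion 1 of protocol 3.6.1).
4. **Saturations below 80%.** Protocol Table 1-2, footnote e, records the exact value. SAP 1.2 and 4.2 record only that it was below 80%, which can make a fall unscorable. Use the exact value, or state how the category is scored.
5. **ECMO.** The SAP row has no measured parameter, so reversing it would copy an undefined criterion. Define one, or report these patients descriptively.

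The cost is an SAP revision and a protocol amendment, which protocol section 8 requires for major changes to the primary outcome definition. It should be done before the blind is broken. If the blind is already broken, section 8 requires the deviation to be described and justified in the final report. No extra visits are needed: saturation, respiratory rate, oxygen demand and oxygenation index are scheduled at STOP Visits 2 and 5 (protocol Table 1-2). Whether the recorded values suffice depends on point 4.

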## 8 STATISTICS

Details of the statistical analysis of the data collected in this trial will be documented in a Statistical Analysis Plan (SAP) that will be generated by IZKS Mainz and finalized before closing the data base and prior to breaking the blind. The SAP is based on the protocol including all amendments. The document may modify the plans outlined in this protocol; however any major modifications of the primary outcome definition and/or its analysis will also be reflected in a protocol amendment. Any deviation from the original statistical plan must be described and justified in the final report. The statistical analysis will be conducted by means of SAS®.

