1.2 Study Design

[figure not shown]
[figure not shown]
This study is an explorative, prospective, randomized, double-blind, placebo controlled investigation of hydroxychloroquine (HCQ) in pediatric ILD. The treatments are organized in START and STOP blocks, which can be initiated in sequence, as needed by the subjects. Each patient can participate in each block, but only once in each block.

In the START block subjects are randomized to parallel-groups, then the placebo group is switched to active drug.

In the STOP block, subjects on HCQ are randomized into parallel-groups treated with placebo or HCQ to investigate the withdrawal of HCQ for assessment of its efficacy.

It is planned to assess >100 subjects for eligibility and to allocate 80 subjects. An equal distribution between START and STOP blocks is expected.

Study flow chart

Trial schedule START HCQ Block

Visit	Screening evaluations and Visit 1	Visit 2	No Visit	Visit 3	No Visit	Visit 4
Action	„Start of baseline“	“End of baseline“ + Day 1 of treatment	Every 7 days at home + web/tele feed-back	End of 1 st Tx period	Every 7 days at home + web/tele feed-back	“End of trial“
Trial day	-28 to -3	1		28 (-4, +7)		56 (-4, +7)
Demographics (e.g. sex, age, race)	X					
Patient information, informed consent	X					
Previous and concomitant diseases	X	X		X		X
Previous and concomitant treatments	X	X		X		X
Inclusion/exclusion criteria	X					
Pregnancy test ^k	X			X		X
Randomization ^l	X					
Physical examination	X	X		X		X
Vital signs (BP, pulse, temp, cardiotoxicity, hypoglycaemia)	X	X		X		X
ECG	X*			X		X
Ophthalmologic review ^m	X*					
Lab ⁿ (GOT/GPT/Crea/BUN/CK/GGT/LDH/BB/DIFF drug level /save EDTA, blood glucose)	X*			X		X
pO ₂ , pCO ₂ (capillary)	X	X***		X***		X***
Primary outcome ^e O ₂ -sat. in room air	X	X	-	X	-	X
Secondary outcomes						
Respiratory rate, in room air	X	X	X	X	X	X
Retractions	X	X	X	X	X	X
Coughing	X	X	X	X	X	X
Oxygen demand	X	X	X	X	X	X
Chest x-ray scoring for child	X*			X****		
Pulmonary hypertension (Echo)	X*					
Quality-of-life ⁱ	X*					X
Health Economics ^h	X*					X
Weight for height ^b	X*					X
Adverse events		X	X	X	X	X
Additionally in children > 5 years						
FEV1 % predicted (recorded in L) ^d	X	X		X		X
FVC % predicted (recorded in L) ^d	X	X		X		X
6 minute walking distance (meter) ^g	X	X		X		X
O ₂ -saturation before and after 6MWT	X	X		X		X
Borg scale ^j	X	X		X		X
Additionally in ventilated patients						
Oxygenation index (OI)	X	X	X	X	X	X

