2.3 Major Protocol Violations

No per protocol analysis will be done.

3 Study Centres

Recruitment and treatment of subjects is expected to be performed in > 100 trial centres.

4 Analysis Variables

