6.4 Prior and Concomitant Medication/Therapies

Concomitant medication/therapies and pain medication will be coded using the current WHO drug dictionary version and will be presented within ATC-2 and ATC-4 level.

Patients with at least one concomitant medication/therapy will be displayed by number and percentages.

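### SAP 6.6 scores the STOP block with an improvement-only responder table, so the responder count cannot register deterioration after HCQ is withdrawn

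*SAP*

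**What the plan says.** SAP 1.2 describes STOP as a randomised comparison of HCQ with placebo "to investigate the withdrawal of HCQ for assessment of its efficacy". SAP 6.6 names the response rate as the primary variable. Under the sub-heading for both blocks separately it prints a single table:

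- room air or oxygen supplement: SpO2 increase of at least 5%;
- high-flow cannula, ventilated, ECMO: decrease of at least 20%, or support no longer needed.

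Item b) then states "Patients are defined as responder as described in the table above" and sends the count to Fisher's exact test and logistic regression. The SAP has no other responder rule for STOP.

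Protocol 8.3.1 (Tab 3.8-1) has two columns, one for initiation and one for withdrawal. The withdrawal column uses a fall of at least 5% "in O2 Sat, or Increase in resp. rate" of at least 20% for children in room air or on oxygen, and a rise of at least 20% in flow or oxygenation index for the others. The oxygen, high-flow and ventilated rows add "or Support newly needed"; the room-air row does not.

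The protocol synopsis, in wording that covers both blocks, calls a patient a responder "if the oxygen saturation is increased by 5% compared to baseline". Protocol section 8 says that "any major modifications of the primary outcome definition and/or its analysis will also be reflected in a protocol amendment".

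**The concern.** The STOP question is whether children get worse when HCQ is taken away. Under SAP 6.6 a responder is a child who gets better. The two are not mirror images: counting improvements tells the reader nothing about how many of the remaining children were stable and how many relapsed. A real excess of relapses on placebo could be tabulated as equal response rates and read as evidence that stopping HCQ is harmless. Protocol 8.3.1 says that the primary outcome was chosen as a yes/no variable, so the affected quantity is the main measure of the block.

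The SAP table also drops respiratory rate, which Tab 3.8-1 uses for children in room air or on oxygen in both columns. START is affected by that omission too.

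**Working it through.** **The definitions side by side (STOP)**

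| Condition | SAP 6.6 | Protocol Tab 3.8-1, withdrawal |
|---|---|---|
| Room air | SpO2 up ≥5% | SpO2 down ≥5%, or respiratory rate up ≥20% |
| On oxygen | SpO2 up ≥5% | as above, or support newly needed |
| High-flow | flow down ≥20%, or support stopped | flow up ≥20%, or support newly needed |
| Ventilated | oxygenation index down ≥20%, or support stopped | index up ≥20%, or support newly needed |
| ECMO | down ≥20%, or support stopped | no row |

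**Single-child check.** A fall in SpO2 from 96% to 85% is (85 − 96)/96 = −11.5%. Tab 3.8-1 scores it as an event. SAP 6.6 scores it as a non-responder, the same as no change.

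**Ceiling.** SpO2 cannot exceed 100%, so a relative rise of 5% needs a baseline of at most 100/1.05 = 95.2%. If 5% means percentage points, the limit is 95%. A child in room air or on oxygen who starts above that cannot be a responder on the SAP table.

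**Arm size.** 80 patients (Protocol 8.1), equal split between blocks (3.2) and 1:1 allocation (3.5.1) give 80/2/2 = 20 per arm. The protocol has no formal sample size calculation, so there is no planned power to reproduce. All event rates below, the 10 per arm and the 0.05 threshold are assumptions.

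**Example counts, 20 per arm, two-sided Fisher.** Suppose 9 placebo and 2 HCQ children deteriorate and nobody improves.

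- SAP 6.6: 0/20 v 0/20, p = 1.0, and a logistic model with no events has nothing to fit.
- Tab 3.8-1: 9/20 v 2/20 = 45% − 10% = 35 points, p = 0.031.

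**Chance of p ≤ 0.05 under Tab 3.8-1**, summing exact binomial probabilities over all outcomes:

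| True deterioration, placebo v HCQ | 20 per arm | 10 per arm |
|---|---|---|
| 40% v 10% | 0.49 | 0.15 |
| 50% v 10% | 0.74 | 0.30 |

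**Chance of p ≤ 0.05 under SAP 6.6, 20 per arm.** This depends only on improvement rates, whatever the relapse rates:

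| True improvement, HCQ v placebo | Chance |
|---|---|
| 0% v 0% | 0 |
| 5% v 5% | 0.002 |
| 10% v 10% | 0.012 |
| 10% v 0% | 0.043 |

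**Sensitivity to background noise.** The respiratory-rate criterion is joined by *or*, so it may add events unrelated to treatment. If it adds an independent 20% in both arms:

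- placebo: 0.40 + 0.60 × 0.20 = 0.52
- HCQ: 0.10 + 0.90 × 0.20 = 0.28

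At 20 per arm the chance falls from 0.49 to 0.24. For 50% v 10% the rates become 60% v 28% and the chance falls from 0.74 to 0.40.

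**The case against.** **The SAP follows the synopsis.** This stands. A reader might infer that the SAP changed the primary outcome without the amendment that Protocol section 8 promises. The documents do not support so firm a charge, because the one-direction rule is already in the synopsis. The defect begins as a conflict inside the protocol, and the SAP took the side that does not fit a withdrawal design. Section 8.3.1 is the only place with a rule written specifically for withdrawal.

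**Other analyses register a fall.** This also stands. SAP 6.6 compares relative change from Visit 2 to Visit 5, and SAP 6.7.1 covers absolute SpO2, respiratory rate and oxygen requirement. It would be wrong to infer that the STOP analysis as a whole is blind to deterioration.

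**The trial is exploratory and the figures favour the criticism.** Partly right. The 0 v 0 result follows from assuming that nobody improves, and the background calculation shows that Tab 3.8-1 can itself be diluted. The p-values measure information lost and are not a decision rule. Even so, an exploratory count should register the event that the block studies.

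**Would the corrected count be biased by added treatment?** A reader might infer that drugs started after a relapse hide it by Visit 5 and pull STOP towards no difference. The documents do not establish this. Protocol 4.1.10 bars steroid pulses and requires a stable oral dose. Room-air SpO2 and the support criterion largely cover added oxygen. SAP 6.7.1 compares cumulative steroid equivalents between arms, and SpO2 is also measured at Visits 3 and 4. The bias needs more added treatment on placebo, and no rates are given. What remains is that SAP 6.4 only codes and tabulates medication ("Concomitant medication/therapies and pain medication will be coded using the current WHO drug dictionary version"), that SAP 2.3 says "No per protocol analysis will be done", and that no rule covers a Visit 5 value taken after such treatment. That justifies an optional sensitivity analysis and no more.

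**Conclusion.** The concern holds for the STOP responder count. As SAP 6.6 is written, Fisher's test and the logistic model compare improvement rates in a block designed to detect worsening, and relapses do not enter the count. This follows from the two tables and needs no assumption. It does not extend to the continuous comparison or the secondary variables.

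The size depends on assumed rates. With 9 v 2 deteriorating and none improving, the difference shown goes from 35 points to zero. Under a true 40% v 10%, Tab 3.8-1 gives about a 0.49 chance of p ≤ 0.05 at 20 per arm, or about 0.24 with the assumed respiratory-rate background. The SAP count gives at most 0.043 in the improvement scenarios tried. The correction should be made before unblinding, with the gaps in Tab 3.8-1 closed at the same time.

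**What to change.** 1. In SAP 6.6, define the STOP event by the withdrawal column of Tab 3.8-1 and label it *deteriorated*, stating that a higher rate on placebo favours HCQ.
2. Add new need for support to the room-air row, where a child first needing oxygen or ventilation would appear. State a matching rule for ECMO, which the SAP lists and Tab 3.8-1 does not.
3. For START, use the full initiation column, including a respiratory-rate decrease of at least 20%, so that both blocks follow the same table.
4. Align the synopsis with section 8.3.1 and record the clarification as section 8 requires.
5. Optional and minor: one sensitivity analysis, fixed by blinded review, scoring as deteriorated any STOP child with added drug treatment for the lung disease, or withdrawal or death for worsening, before Visit 5. Withdrawal matters because Protocol 3.6.3 allows it for life-threatening aggravation and SAP 5.1 plans no substitution of missing values. Keep as-measured ITT as the main analysis.

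The cost is SAP and synopsis wording, plus one blinded listing review if item 5 is adopted. SpO2, respiratory rate, oxygen demand and concomitant treatments are already collected at every STOP site visit. The downside of item 5 is that treatment given for another reason may count as failure; the as-measured analysis beside it shows how much that matters. Using the *or* rule on respiratory rate may add background events, so the components should also be tabulated separately.
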